### Study Synopsis

This study will include adult outpatients 18-65 years of age with major depressive disorder (MDD) with subjective reporting of cognitive dysfunction treated with flexible-dose vortioxetine (5-20 mg/day) for eight weeks. Following completion of the informed consent process, this study will consist of a screening period (visit 1) of 2-14 days to assess inclusion/exclusion criteria. Subjects who continue to meet inclusion criteria at baseline (visit 2) will begin the assessment and treatment phase of the study.

The first EEG/BNA (BNA) will be performed at the screen visit. Subsequent BNA will be at baseline, 2-weeks after the start of treatment, and at the end of 8 weeks of treatment (or early termination).

The Schedule of Events (Appendix I) shows detailed study procedures that will be performed at each visit. The table below clarifies the schedule of dosing and attendant BNA tests.

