#### **Rationale for the Proposed Study:**

Vortioxetine has been shown to improve core depressive symptoms and improve cognitive function in adult outpatients with MDD and subjective complaints of cognitive function. This pilot study is intended to evaluate the extent to which BNA technology can provide clinically valuable information and provide information toward designing a subsequent confirmatory study that will further elucidate the effect of vortioxetine on MDD and cognitive function in this population. This exploratory study will ascertain the acute changes in core depression symptoms, cognitive function, tolerability, and safety using flexible-dose vortioxetine in adult outpatients with MDD with subjective complaints of cognitive functioning, as measured by BNA changes and standard outcome measures for depression and cognition.

Data suggest that the impact of vortioxetine on cognition in MDD may be independent of the antidepressant effect, perhaps through a centrally-mediated pathway different from that involved in the antidepressant effects. This study will investigate the effect of vortioxetine on cognitive dysfunction more broadly covering specific measures of attention, executive functioning and psychomotor speed, as well as assess its effect on core depressive symptoms, function and global change. The number of subjects treated in this study is generally accepted for exploratory studies and intended to demonstrate 1) improvement in cognition and efficacy in conventional MDD symptom domains, 2) improvement in cognition but no antidepressant efficacy in conventional MDD symptom domains, and, 3) no improvement of cognition and no antidepressant efficacy in conventional MDD symptom domains. We predict distinct patterns in brain network activity among these subgroups. This preliminary data is expected to provide greater insight into understanding the direct versus indirect antidepressant effects

of acute treatment with vortioxetine on cognition in MDD, and provide a basis for future clinical trials and applications.

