**Main Criteria for Exclusion:**

- The subject has a score of  $\geq 70$  on the DSST at the Baseline Visit.
- Failure to respond to or inability to tolerate an adequate trial of vortioxetine in the past.
- Exposure to an investigational compound 30 days prior to enrollment
- Exposure to any psychoactive or otherwise excluded medication within five half-lives of the baseline visit or during the study. Excluded medications include: antidepressants, anxiolytics, anticonvulsants, barbiturates, chloral hydrate, lithium, antipsychotics, benzodiazepines, hypnotics, MAO-Inhibitors, muscle relaxers, triptans, centrally-acting antihistamines, central alpha-2 agonists, decongestants, psychostimulants, dopamine agonists, opioid pain medications, oral corticosteroids, L-methylfolate, SAMe, 5-HTP, St. John's Wort.
- The subject has 1 or more of the following:
  - Primary psychiatric disorder other than MDD as defined in the DSM-IV-TR (as assessed by the MINI, Version 6.0.0).

- Current or history of attention deficit hyperactivity disorder (ADHD), pervasive developmental disorder, manic or hypomanic episode, schizophrenia, or any other psychotic disorder, including major depression with psychotic features, mental retardation, organic mental disorders, or mental disorders due to a general medical condition as defined in the DSM-IV-TR.
- Current diagnosis of alcohol or other substance abuse or dependence (excluding nicotine or caffeine) as defined in the DSM-TV-TR that has not been in sustained full remission for at least 6 months (for abuse) and 12 months (for dependence) prior to Screening.
- Positive urine drug screen prior to Baseline.
- Presence or history of a clinically significant neurological disorder (including epilepsy) or severe head injury, or any condition that has caused an abnormal EEG or that may interfere with an EEG recording in the opinion of the investigator.
- Neurodegenerative disorder (Alzheimer Disease, Parkinson Disease, multiple sclerosis, Huntington Disease, etc).
- Any unstable medical condition as determined by the principal investigator (PI).
- Any DSM-IV Axis II disorder that might compromise the study as determined by the PI.
- The subject has any other disorder for which the treatment takes priority over treatment of MDD or is likely to interfere with study treatment or impair treatment compliance.

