### **Secondary Efficacy Analyses**

Change from Baseline in TMT A, TMT B, , PDQ, MGH-CPFQ, UPSA, percentage of productivity loss (WLQ), MADRS, CGI-S, and CGI-I will be analyzed at all time points (where rated) using ANCOVA model similar to the one described above for the primary endpoints.

MADRS responders (defined as a >50% decrease from Baseline), MADRS remission (defined as a MADRS total score <10). CGI-S remission (CGT-S2), and CGI-I response (CGI-I2) will be analyzed at all time points by logistic regression, adjusting for baseline score and treatment.

Proportion of cognitive dysfunction improvement that is not due to an improvement in depressive symptoms will be analyzed using a path analysis with change from Baseline in DSST score and change from Baseline in MADRS total score as endogenous variables.

C-SSRS will be summarized at all time points using descriptive techniques.

All statistical tests will be 2-sided and at the 5% level of significance. Ninety-five percent confidence limits will be presented together with the p-values.

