**APPENDIX I - SCHEDULE OF EVENTS**

Visit #	Screen 1	Baseline 2	3	4	5	6	7	8	9	10 (or ET)
Day	-2 to -14	0	7	14	21	28	35	42	49	56
Week	-1 to-2	0	1	2	3	4	5	6	7	8
Informed Consent	X									
Incl/Excl Criteria	X	X								
MINI	X									
ASRS	X									
Medical and Psychiatric History	X									
Demographics	X									
Physical Exam	X									
Laboratory tests, urinalysis, urine pregnancy test and urine drug screen 	X									
Vital signs and weight 	X	X	X	X	X	X	X	X	X	X
Height		X								
12-Lead ECG	X									
HDRS (28-item)	X	X	X	X	X	X	X	X	X	X
QIDS-SR-16	X	X	X	X	X	X	X	X	X	X
MADRS	X	X	X	X	X	X	X	X	X	X
DSST	X									X
UPSA	X									X
TMT-A AND TMT-B	X									X
Stroop Test	X									X
MGH-CPFQ	X	X	X	X	X	X	X	X	X	X
PDQ	X	X	X	X	X	X	X	X	X	X
CGI-S	X	X	X	X	X	X	X	X	X	X
CGI-I			X	X	X	X	X	X	X	X
WLQ	X	X	X	X	X	X	X	X	X	X
C-SSRS 	X	X	X	X	X	X	X	X	X	X
Concomitant therapy	X	X	X	X	X	X	X	X	X	X
Study drug dispensed		X	X	X	X	X	X	X	X	
Study drug accountability			X	X	X	X	X	X	X	X
Adverse events	X	X	X	X	X	X	X	X	X	X
EEG (BNA reading)	X	X		X						X

may be repeated at investigator's discretion

including body temperature (oral), blood pressure and pulse.

C-SSRS lifetime version at screen only; Since Last Visit version at V2-10

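### If Appendix I is followed, DSST change starts at Screen and MADRS change at Visit 2, so the path analysis can misplace mood-linked DSST change from the screening period

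*Combined protocol and SAP*

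**What the plan says.** - **Analysis.** Secondary Efficacy Analyses sets the target as the "Proportion of cognitive dysfunction improvement that is not due to an improvement in depressive symptoms", to be estimated by a "path analysis with change from Baseline in DSST score and change from Baseline in MADRS total score as endogenous variables". It names no exogenous variable and does not say which visit supplies the baseline value for each scale.
- **Baseline.** The Study Synopsis ties the word to Visit 2: "Subjects who continue to meet inclusion criteria at baseline (visit 2) will begin the assessment and treatment phase". The visit tables put that visit at Day 0. Before it, "this study will consist of a screening period (visit 1) of 2-14 days".
- **Schedule.** In "APPENDIX I - SCHEDULE OF EVENTS" the DSST row is marked only at Screen and at Visit 10 (or early termination). The MADRS row is "MADRS X X X X X X X X X X", that is, all ten visits, including Screen and Visit 2.
- **Conflicting text.** Main Criteria for Exclusion removes subjects who score 70 or more "on the DSST at the Baseline Visit". Appendix I repeats the eligibility check at Visit 2, and item 5b of the Secondary Outcomes refers to a baseline DSST.
- **Hypothesis.** The Rationale states: "Data suggest that the impact of vortioxetine on cognition in MDD may be independent of the antidepressant effect".

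**The concern.** The path analysis divides one change (DSST) by reference to another (MADRS). The division is meaningful only if both changes cover the same period. On the Appendix I schedule, with MADRS change taken from Visit 2, they do not. DSST change includes the screening period and MADRS change leaves it out. Any DSST change that goes with mood change between Screen and Visit 2 is then in the outcome but not in the mediator, so it is counted as unrelated to mood.

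The share bears directly on the Rationale's idea that the cognitive effect may be separate from the antidepressant effect. If mood improves before dosing, the mismatch pushes the share towards that idea. If mood worsens, it pushes the other way. A larger sample would not remove the shift, which matters for a pilot meant to inform a confirmatory study.

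**Working it through.** The documents give no figure for this share, for MADRS or DSST change, or for mood change during screening. There is nothing to reproduce, and every magnitude below rests on stated assumptions.

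**Step 1: the two periods.** Visit 10 is Day 56 and Screen is Day -2 to -14.
- MADRS change from Visit 2: 56 days.
- DSST change from Screen: 56 + 2 = 58 to 56 + 14 = 70 days.
- Screening as a fraction of the DSST period: 2/58 = 3% to 14/70 = 20%.

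**Step 2: the algebra.** Let S be MADRS change from Screen to Visit 2 and T the change from Visit 2 to Visit 10. Suppose DSST change from Screen = d + b(S + T) + error, where d is the part separate from mood. The true mood-mediated share is m = b(E[S] + E[T]) / (d + b(E[S] + E[T])). If S and T are uncorrelated, regressing DSST change on T alone still gives slope b, but b·E[S] moves into the intercept. The shift in the share not attributed to mood is

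m × E[S] / (E[S] + E[T]).

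**Step 3: numbers.** Assumed: E[T] = -16 MADRS points, m from 0.3 to 0.7, no measurement error. Shifts are in percentage points.

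| E[S] | E[S]/(E[S]+E[T]) | m = 0.3 | m = 0.5 | m = 0.7 |
|---|---|---|---|---|
| 0 | 0 | 0 | 0 | 0 |
| -1 | 1/17 = 0.059 | +1.8 | +2.9 | +4.1 |
| -2 | 2/18 = 0.111 | +3.3 | +5.6 | +7.8 |
| -4 | 4/20 = 0.200 | +6.0 | +10.0 | +14.0 |
| +2 | 2/(-14) = -0.143 | -4.3 | -7.1 | -10.0 |

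The ceiling for the falls is m = 1, where all DSST gain is mood-mediated. On a 15-point treatment-period fall this gives 2/17 = 12 points for a 2-point screening fall and 4/19 = 21 points for a 4-point fall.

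**Step 4: check by simulation.** Further assumptions: total DSST gain 8 points; SDs of 3 for S, 8 for T and 6 for residual DSST. With E[S] = -2 and m = 0.5, 2,000,000 simulated subjects gave a share of 0.555 with MADRS from Visit 2 and 0.500 with MADRS from Screen, against a true 0.500.

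**Step 5: measurement error.** With an error SD of 3 on each MADRS rating, the Visit 2 version exceeded the Screen-aligned version by 0.7 to 1.5 points even at E[S] = 0. Both were also too high: 0.609 and 0.598 against a true 0.500 at m = 0.5. Alignment removes the mismatch but not this attenuation.

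**Step 6: sampling error.** In 4,000 simulated trials of 40 subjects (E[S] = -2, m = 0.5, no measurement error), the central 95% of the estimated share ran from about 0.00 to 1.05, against a shift of 5.6 points.

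**The case against.** The strongest reply is that the plan does not specify a mismatch. The exclusion criterion needs a DSST score at the Baseline Visit. If one is taken there, both changes can start at Visit 2 and the problem disappears. The Visit 2 start for MADRS is itself an inference from the visit label. This stands. A reader might infer from Appendix I that DSST change can only start at Screen and that mood change in screening is certain to be misassigned; the documents do not support that. What remains is a contradiction about DSST timing and an undefined baseline, which leave an analyst free to use unmatched starting points.

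Second, subjects must still qualify at Visit 2, and the inclusion criteria require a MADRS of at least 26. This limits the screening falls possible among treated subjects, but it does not fix the mean change at zero.

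Third, the shift is small beside sampling error in a pilot with no sample size calculation. Aligned periods would also still leave practice and time effects in the remainder, because no control arm is described. Both points stand and limit the importance of this one. They do not justify keeping a systematic error that can be removed at almost no cost.

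A reader might also take this share as the trial's only numerical evidence on cognition apart from mood. Item 4 of the Secondary Outcomes groups subjects by antidepressant efficacy and DSST improvement, which gives counts on the same question. If the starting visits differ, those groups inherit the mismatch.

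**Conclusion.** The point holds conditionally. If Appendix I is followed and MADRS change starts at Visit 2, the path analysis compares changes over different periods, and mood-linked DSST change during screening enters the share not attributed to mood. The direction depends on mean mood change in screening, which the documents do not give. It is therefore not established that the analysis favours the protocol's hypothesis.

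Under the Step 3 assumptions, a 2-point screening fall adds about 3 to 8 percentage points, a 4-point fall adds 6 to 14, and a 2-point rise subtracts 4 to 10. The 12 and 21 points at full mediation are ceilings, not expected values. The zero for stable mood requires S and T to be uncorrelated and the MADRS to be free of measurement error. This is a modest, avoidable flaw in one secondary analysis and the related groupings. It does not affect a MADRS or DSST change analysed on its own.

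**What to change.** 1. Reconcile Main Criteria for Exclusion with Appendix I on whether a DSST is taken at Visit 2, and define the analysis baseline for each scale.
2. Add to Secondary Efficacy Analyses that DSST change and MADRS change must start at the same visit: Visit 2 for both if a Visit 2 DSST is taken; otherwise the Screen MADRS with the Screen DSST, with the Visit 2 MADRS as a sensitivity analysis. Apply the same rule to the groups in item 4 of the Secondary Outcomes.
3. State beside the result that practice and time effects remain in the share not attributed to mood.

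The cost is a few sentences. The Screen MADRS is already scheduled, so alignment needs no new assessment. If the reconciliation adds a Visit 2 DSST, the protocol puts that test at about 5 minutes. The downside of the Screen option is that this analysis would use a different MADRS baseline from a Visit 2 baseline in the primary and responder analyses, and both changes would include 2 to 14 untreated days. The report should say so.

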### **Outcome Definitions**

- Remission (Primary Remission Criteria)
  - MADRS total score  $\leq$  10; CGI-I  $<$  2
- Remission (Secondary Remission Criteria)
  - Score  $\leq$  7 of first 17 items of the HDRS (28-item)
  - QIDS-SR16 total score  $<$  5
- Asymptomatic Remission
  - MADRS total score  $\leq$  4
- Response (Primary Response Criteria)
  - $\geq$ 50% decrease in MADRS total score from baseline
- Response (Secondary Response Criteria)
  - $\geq$ 50% decrease from baseline of first 17 items of the HDRS (28-item)
  - $\geq$ 50% decrease from baseline in total score of HDRS (28-item)
  - $\geq$ 50% decrease from baseline in total score of QIDS-SR 16
  - $\geq$ 50% decrease from baseline in total score of MGH-CPFQ
- Non-Remitted (Primary)
  - MADRS total score  $>$  10
- Non-response
  - Change in MADRS total score from baseline  $<$  25%, and MADRS total score  $>$  10
- Inadequate response
  - Change in MADRS total score from baseline 25-49%, and MADRS total score  $>$  10

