    - i. Subjects meeting antidepressant efficacy criteria (based on response and remission criteria for MADRS, HRSD, QIDS) and improvement in cognition (based DSST).
    - ii. Subjects failing to meet antidepressant efficacy criteria (based on response criteria for MADRS, HRSD, QIDS) but show improvement in cognition (based on DSST).
    - iii. Subjects failing to meet antidepressant efficacy criteria (based on response criteria for MADRS, HRSD, QIDS) and failing to show improvement in cognition (based on DSST).
    - iv.
    - v.
- 5. To explore changes in BNA patterns in MDD with cognitive dysfunction prior to receiving treatment with vortioxetine and:
  - a. Severity of MDD as measured by baseline MADRS total score, QIDS-SR-16 total score, HDRS-28 item total score and CGI-Severity.
  - b. Severity of cognition dysfunction and functionality as measured by baseline DSST, TMT-A/B, TMT-B, Stroop, MGH-CPFQ total score, UPSA, WLQ.
  - c. Prediction of achieving symptomatic remission of MDD as measured by remission status on MADRS total score, HDRS-17 total score and CGI-Improvement (1 or 2)
  - d. Prediction of cognitive improvement measured by DSST score; cutoff 70% improvement from baseline.
- 6. Explore relationship with changes in BNA patterns in remitted vs. non-remitted subjects after 8 weeks of treatment with vortioxetine as measured by MADRS total score, HDRS-17 total score, QIDS total score,, and CGI-Improvement.
- 7. Assess safety and tolerability of 8 weeks open-label, flexible-dose vortioxetine in all subjects for:
  - a. Spontaneously reported adverse events
  - b. Clinical safety laboratory tests (when indicated, vital signs, weight, EKGs and physical exam)

- c. Evaluate relationship between adverse events after 2 and 8 weeks of treatment with changes in BNA patterns for nausea, worsening of baseline suicidal ideation (as measured by MADRS item 10, HDRS-17 item 2 and C-SSRS)

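### The primary definitions of remitted and non-remitted are not complements, and the printed remission limits differ between sections

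*Combined protocol and SAP*

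**What the plan says.** All references are to the combined protocol and SAP.

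- **Outcome Definitions.** Under "Remission (Primary Remission Criteria" the rule is "MADRS total score $\leq$ 10; CGI-I $<$ 2", on one line with a semicolon between the two parts. Under "Non-Remitted (Primary" the rule is a MADRS total above 10, with no CGI-I condition.
- **Secondary Outcomes, items 1 and 2.** Remission is a MADRS total below 11, with no CGI-I condition.
- **Secondary Outcomes, item 5c.** Prediction of remission is to be judged by "remission status on MADRS total score, HDRS-17 total score and CGI-Improvement (1 or 2").
- **Secondary Outcomes, item 6.** The plan is to "Explore relationship with changes in BNA patterns in remitted vs. non-remitted subjects after 8 weeks of treatment with vortioxetine", using MADRS, HDRS-17, QIDS and CGI-Improvement.
- **Secondary Efficacy Analyses.** The logistic regression uses "MADRS remission (defined as a MADRS total score <10"). The same sentence has "CGI-I response (CGI-I2"), with its comparison sign missing.
- **Primary Efficacy Analysis.** BNA change is also to be analysed in groups formed by endpoint status, with remission given as an example.

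**The concern.** A comparison of remitted with non-remitted subjects needs two classes that exclude each other and together cover everyone assessed. Here one class carries a CGI-I condition and the other does not, so an analyst who follows the text literally has subjects with no group, or with two. The analyst must then decide where they go, possibly after seeing the BNA results.

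The printed limits add a second problem: the same subject can be a remitter under one section and not under another. With 40 subjects and results meant to help design a confirmatory study, moving a few subjects could change a group comparison noticeably.

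**Working it through.** The plan states no figure to reproduce, so the check enumerates every possible pair of scores under each reading.

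**Inputs.** MADRS total runs from 0 to 60, giving 61 values (description of the MADRS). CGI-I runs from 1 to 7 (Clinical Global Impression Scales; Other Risks), so a limit of below 2 admits only a rating of 1, very much improved. Number of pairs: 61 × 7 = 427. Non-remitted is MADRS 11 to 60: 50 × 7 = 350 pairs. That leaves 11 × 7 = 77 pairs with MADRS 0 to 10.

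| Reading of remission | Remitted | In neither class | In both classes |
|---|---|---|---|
| MADRS ≤10 and CGI-I <2 | 11 × 1 = 11 | 77 − 11 = 66 | 0 |
| MADRS ≤10 and CGI-I 1 or 2 | 11 × 2 = 22 | 77 − 22 = 55 | 0 |
| MADRS ≤10 or CGI-I <2 | 77 + 50 = 127 | 0 | 50 × 1 = 50 |
| MADRS ≤10 or CGI-I 1 or 2 | 77 + 100 = 177 | 0 | 50 × 2 = 100 |
| MADRS <10 alone | 10 × 7 = 70 | 77 − 70 = 7 | 0 |
| MADRS ≤10 alone (same as <11) | 77 | 0 | 0 |

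The gap comes from the asymmetry within Outcome Definitions. The CGI-I limit only changes its size: the 11 pairs with MADRS 0 to 10 and CGI-I 2 count as remitted under item 5c's limit and fall in neither class under Outcome Definitions. The limit of below 10 in Secondary Efficacy Analyses leaves a subject scoring exactly 10 outside both classes.

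**From pairs to subjects.** Pairs are not equally likely. Entry requires MADRS of at least 26, so reaching 10 is a fall of at least (26 − 10)/26 = 61.5%. Every subject in the gap is therefore also a primary responder (a fall of 50% or more). A rating of 2, much improved, is plausible for such a subject; ratings of 4 to 7 are unlikely.

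**Illustration, on assumptions not in the documents.** Suppose 20% to 50% of 40 subjects, that is 8 to 20, end with MADRS 10 or lower.

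- CGI-I below 2 required, and 10% to 50% of them not rated 1: from 8 × 0.10 = 0.8 to 20 × 0.50 = 10, so about 1 to 10 subjects unclassified.
- CGI-I 1 or 2 required, and 0% to 5% of them rated 3 or worse: from 0 to 20 × 0.05 = 1.0, so 0 to 1 subject.

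**The case against.** The strongest reply is that the semicolon may separate two criteria to be applied instrument by instrument. Item 6 lists four instruments, item 5c lists three, and two other sections define MADRS remission without CGI-I. On that reading the MADRS comparison in Outcome Definitions is at most 10 against above 10, an exact partition. This reading is tenable. But the shared line reads more naturally as a joint condition, because the secondary criteria below it stand on separate lines. Nor does this reading resolve the score of exactly 10, or say what non-remitted means on CGI-I.

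A second reply is that signs were lost in reading the text, as they visibly were in "CGI-I response (CGI-I2"). The CGI-I limit could then be at most 2, agreeing with item 5c, and the MADRS limit of below 10 could be at most 10. This cannot be excluded, although the ≤ sign survives on the same line as CGI-I below 2. If it is so, the conflicts between sections vanish and the gap shrinks to 0 to 1 subject on the assumptions above, but the two classes are still not complements under a joint reading.

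A reader might also infer that the gap subjects are dropped, leaving a comparison of extremes that exaggerates the BNA difference. The documents do not support this. Nothing says these subjects are excluded. A subject with MADRS 11 stays in the non-remitted group, so only the low-MADRS side would be thinned. And the Primary Efficacy Analysis text allows that network changes may not follow symptoms or neurocognitive scores at all, so the direction of any bias is unknown.

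**Conclusion.** Wrong as written, with limited reach. As a joint rule, primary remission leaves some score pairs in neither class (66 of 427 at CGI-I below 2, 55 at 1 or 2); as an either-or rule it puts 50 or 100 in both. As printed, the CGI-I limit differs between Outcome Definitions and item 5c, and the MADRS limit in Secondary Efficacy Analyses differs from the other two sections for a score of exactly 10.

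The number of subjects affected is not known. The ranges of 1 to 10 and 0 to 1 of 40 rest wholly on assumed remission and rating rates. The class problem concerns exploratory BNA comparisons; the score-of-10 conflict also decides who counts as a remitter in the secondary logistic regression. The primary analysis of change in MADRS and DSST uses neither class.

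The CGI-I item in Secondary Efficacy Analyses should not be read as a third conflicting remission limit. It is labelled response, its sign is missing, and response need not share a cut-off with remission.

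**What to change.** Use one primary remission definition in Secondary Outcomes, Secondary Efficacy Analyses and Outcome Definitions. MADRS of at most 10 alone would do: it equals the below-11 limit already in Secondary Outcomes and leaves 0 of 427 pairs unclassified or double-classified. Change the below-10 limit in Secondary Efficacy Analyses to match, and define non-remitted as every assessed subject who does not meet the remission definition.

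If the CGI-I condition is kept, replace the semicolon with 'and', use one CGI-I limit in item 5c and Outcome Definitions, and make non-remission the exact complement. Leave the CGI-I response criterion in Secondary Efficacy Analyses out of this change.

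The cost is wording in those sections. No additional data are needed. The choice should be fixed before the BNA results are examined.
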